### 12.6 Analysis of Primary Objective

Subjects will be assessed for radiographic progression as described in section 8. Time from first dose of ADT to radiographic progression or death, whichever occurs first, will be calculated for each subject. For subjects who discontinue study treatment due to reasons other than death or investigator assessed progression, every effort will be made to continue tumor assessments on schedule until radiographic progressive disease or subject death. Subjects who do not have radiographic progression or death will be censored at their last measure for radiographic progression. The primary hypothesis test will be conducted at a one-sided 0.1 significance level using a stratified log-rank test. Kaplan-Meier methods will be used to report rPFS graphically by arm including the median rPFS and 12 and 24 month rPFS proportions in the ITT population. The log-rank test without stratification will be used as a sensitivity analysis.

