
STATISTICAL CONSIDERATIONS
	
Primary Analysis Subjects will be assessed for radiographic progression as described in Section 8. Time from first dose of ADT to radiographic progression or death, whichever occurs first, will be calculated for each subject. For subjects who discontinue study treatment due to reasons other than death or investigator assessed progression, every effort will be made to continue tumor assessments on schedule until radiographic progressive disease or subject death. Subjects who do not have radiographic progression or death will be censored at their last measure for radiographic progression. The primary hypothesis test will be conducted at a one-sided 0.1 significance level using a stratified log-rank test. Kaplan-Meier methods will be used to report rPFS graphically by arm including the median rPFS and 12 and 24 month rPFS proportions in the ITT population. The log-rank test without stratification will be used as a sensitivity analysis.
 
Secondary analysis Toxicity will be described within each arm by type, maximum grade and frequency among the safety population. The proportion of subjects in each arm with skeletal related events and secondary neoplasms will be reported individually and a mid p-value test will compare the proportions between arms.
 
Time to castration resistance (TTCR), PSA progression free survival (PCWG2 criteria), and Overall Survival (OS) will be reported by arm using Kaplan-Meier methods and tested using the stratified log-rank test. The 2 -year PSA PFS and OS proportions with 90% confidence intervals and median time to castration resistance will be reported using Kaplan-Meier methods. Analyses will be completed on the ITT population.
 
Binomial proportions with 90% binomial confidence intervals of subjects who achieve PSA <math>\leq</math> 0.2 ng/mL at 7 months after treatment initiation will be reported by arm. Similarly, the proportions and associated confidence intervals of subjects who achieve PSA <math>\leq</math> 4 ng/mL at 7 months after treatment initiation will be

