12. For late induction subjects, Cycle 1 Day 1 will occur after screening and upon completion of eligibility. C1D1 lab testing need not be repeated if completed within 7 days of starting protocol therapy. For early induction subjects, C1D1 occurs prior to screening; documentation of initiation of ADT (C1D1) should occur after review of the subject chart and completion of eligibility.
13. For maintenance Cycles 14-17, subjects will continue to be followed every 12 weeks for alkaline phosphatase, PSA values and AE/concomitant medication updates, initiation of new anti-cancer therapy and occurrence of secondary malignancies. This information may be obtained via local treating physician medical records.
14. The end of treatment/follow up column will be utilized for subjects that come off protocol therapy (both Arm A and Arm B) for toxicity or progression. If this occurs, subjects should have an end of treatment visit 30 days ( $\pm$  7 days) after discontinuation of protocol therapy. Subjects will then continue to be followed every 3 months for a total of 2 years from the date of randomization. If a subject withdraws consent, he is deemed "off study" and will NOT be followed further. Follow up may occur via phone call, email or other communication. If available by medical record review, alk phos, PSA, AE/concomitant medication should be obtained.

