### 7.10 End of Treatment (EOT) and Follow Up

The end of treatment/follow up column will be utilized for subjects that come off protocol therapy (radium-223 dichloride if randomized to that Arm and ADT) for toxicity or progression. If this occurs, subjects should have an end of treatment visit 30 days ( $\pm$  7 days) after discontinuation of protocol therapy. Subjects will then continue to be followed every 3 months for a total of 2 years from the date of randomization. Follow up may occur via phone call, email or other communication. If available by medical record review, alk phos, PSA, AE/concomitant medication should be obtained. Testing to be done at the EOT visit:

- Circulating tumor cell's (CTCs)
- Serum bone turnover markers
- Banking Samples: serum, plasma
- Alkaline phosphatase
- PSA

If a subject withdraws consent, he is deemed **“off study”**. “Off study” subjects will not be followed further.

A subject will be discontinued from the protocol specified therapy under the following circumstances:

- If there is evidence of radiologic disease progression or symptomatic deterioration despite castration range serum testosterone level ( $< 50$  ng/dL). Such subjects can go on to other treatment outside the study as clinically indicated including continuation or initiation of radium-223 dichloride therapy. They will remain on follow-up portion of the study for a total of 2 years from the date of randomization.
- If there is development of castration-resistant prostate cancer by PSA criteria in conjunction with castration range serum testosterone level ( $< 50$  ng/dL). Castration resistant prostate cancer is defined as two consecutive increases in PSA over the nadir PSA, at least two weeks apart **AND** an absolute increase of at least 2 ng/mL from the nadir PSA (or from baseline PSA if there was no drop in PSA after starting treatment). Discontinuation of bicalutamide may be attempted at the investigator's discretion in such cases and would NOT constitute going “off treatment”. If no response to bicalutamide discontinuation, such subjects may receive other treatment outside the study as clinically indicated including continuation or initiation of radium-223 dichloride therapy. They will remain on follow-up portion of the study for a total of 2 years from the date of randomization.

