- If a subject requests to discontinue protocol specified therapy for any reason at any time. Subjects can stop protocol therapy at any time (off treatment). Such subjects may receive other treatment outside the study as clinically indicated including continuation or initiation of radium-223 dichloride therapy. However, subjects will continue to be followed for survival status and for secondary malignancies as reported by subjects every 3 months for a total of 2 years from the date of randomization unless they withdraw consent (if consent withdrawn, they will be deemed to be off study).

- If androgen deprivation therapy exhibits unacceptable toxicity. Such subjects may receive other treatment outside the study as clinically indicated including continuation or initiation of radium-223 dichloride therapy. **NOTE:** Subjects off bicalutamide or radium-223 dichloride for toxicity but continuing on LHRH agonist/antagonist or have had surgical castration remain on protocol specified therapy.
- If **ALL** protocol specified therapy is interrupted for > 28 days due to a treatment related adverse event. **NOTE:** A delay of up to 7 days in administering the scheduled dose of LHRH agonist or LHRH antagonist is allowed. A delay of up to 56 days in administering the scheduled dose of radium-223 dichloride is allowed if it is due to inadequate hematologic parameters or drug supply issues.

All reasons for protocol therapy discontinuation must be clearly documented.

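### Section 12.6 promises tumor assessments after treatment stops, but section 7 schedules none; if sites follow section 7, rPFS censoring is tied to worsening disease

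*Combined protocol and SAP*

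**What the plan says.** **The promise.** Section 12.6 reads "For subjects who discontinue study treatment due to reasons other than death or investigator assessed progression, every effort will be made to continue tumor assessments", and the synopsis has the same sentence, which goes on: "every effort will be made to continue tumor assessments on schedule until radiographic progressive disease or subject death". Subjects without radiographic progression or death are censored at their last radiographic assessment (8.8, 12.6).

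**What section 7 provides.**
- Section 7.10 lists the reasons for ending protocol therapy. One is "If there is development of castration-resistant prostate cancer by PSA criteria in conjunction with castration range serum testosterone level". PSA progression is not an rPFS event under 8.8. Of these subjects 7.10 says "They will remain on follow-up portion of the study for a total of 2 years from the date of randomization". They may be treated outside the study, and starting or continuing radium-223 is expressly allowed.
- Of follow-up after treatment, 7.10 says "Follow up may occur via phone call, email or other communication".
- For those who stop at their own request, "subjects will continue to be followed for survival status and for secondary malignancies as reported by subjects every 3 months".
- Calendar footnote 14 assigns the End of Treatment and Follow up column to "subjects that come off protocol therapy (both Arm A and Arm B) for toxicity or progression". That column has no mark for CT, MRI, chest imaging or bone scan. The end-of-treatment test list in 7.10 holds CTCs, bone turnover markers, banked samples, alkaline phosphatase and PSA.
- The imaging footnote places CT/MRI at screening, C8D1, C13D1 and C17D28, and bone scans at baseline, C8D1 and after one year.

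**Mitigating text.** Section 7.10 notes: "Subjects off bicalutamide or radium-223 dichloride for toxicity but continuing on LHRH agonist/antagonist or have had surgical castration remain on protocol specified therapy". Trying bicalutamide withdrawal after PSA progression does not count as going off treatment. Sections 8.2.4 and 8.14 ask for efforts to document progression after symptomatic deterioration. The intention-to-treat principle in 12.4 has subjects followed and assessed whatever their compliance.

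**The concern.** Section 8.6 treats PSA progression and radiographic progression as alternative signs of one state, castration resistance. If scanning ends at the first sign, a subject is censored for a reason that plausibly predicts the second. The log-rank test and the Kaplan-Meier estimate both assume that censoring carries no such information.

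Three features of the plan leave this unguarded.
- The exemption in 12.6 is not limited to radiographic progression, and section 8.2 (Progression Criteria) lists PSA progression first. A site could conclude that 12.6 asks for no scans in the very group most at risk.
- The only rPFS sensitivity analysis is an unstratified log-rank test, which uses the same censoring.
- The sample size allows for 10% yearly dropout and has no term for scans that stop at PSA progression.

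No placebo or blinding of treatment is described, so the loss of imaging need not be equal between arms.

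**Working it through.** **1. Which scans are at risk.** Cycles 1-12 last 28 days and later cycles 84 days. Counted from C1D1, C8D1 = 7 × 28 = day 196, C13D1 = 12 × 28 = day 336, and C17D28 = 336 + 4 × 84 + 27 = day 699. A subject who comes off between days 196 and 336 has no later scan in the off-treatment schedule. The visits at risk are C13D1 (CT/MRI and bone scan) and C17D28 (CT/MRI). One who comes off after C13D1 has only the day-699 CT/MRI at risk, because no one has a bone scan scheduled after one year.

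**2. The plan's own figures (12.1).** Events d = (z_α + z_β)² / [p(1−p)(ln HR)²], with one-sided α = 0.10, power 0.90, p = 1/3 and HR = 12/19. This gives (1.2816 + 1.2816)² / [(2/9)(0.4595)²] = 140. Monthly hazards are ln2/12 = 0.0578 and ln2/19 = 0.0365, and dropout is −ln(0.9)/12 = 0.0088. With uniform accrual over 24 months and analysis at month 48, event probabilities are 0.780 and 0.640, so 68 × 0.780 + 136 × 0.640 ≈ 140. The plan reproduces.

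**3. Baseline with follow-up capped at 24 months (7.10).** Event probabilities by 24 months are 0.692 and 0.534, so 68 × 0.692 + 136 × 0.534 ≈ 120 events. Power = Φ(√(120 × 2/9) × 0.4595 − 1.2816) = 0.86. This fall from 0.90 is a separate matter and is not counted here.

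**4. Simulation of lost imaging.** The documents give no rate of PSA progression before radiographic progression, so these inputs are assumptions:
- PSA-progression median 0.6, 0.8 or 1.0 times the rPFS median, PSA HR 0.64 (the figure that section 1.3 gives for castration-resistant disease), and copula correlation 0.5 or 0.8.
- 10% of rPFS events are deaths and always count. Deaths after unseen progression are either counted or not.
- The treatment effect is unchanged after PSA progression.
- Unstratified one-sided 0.10 log-rank test, 2,000 trials per scenario, Monte Carlo standard error about 0.01.

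Progression is seen only at days 196, 336 and 699, and a stated share of subjects with PSA progression first lose all later imaging, equally in both arms:

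| Share losing imaging | Power |
|---|---|
| 0% | 0.84-0.87 (113-114 events) |
| 25% | 0.82-0.85 |
| 50% | 0.79-0.85 |
| 100% | 0.67-0.82 |

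A separate uncapped run with continuous detection gave 140 events and power 0.91 with full scanning, and 120-123 events and 0.84-0.85 when half keep scanning. With all scanning stopped at PSA progression, the control median stayed near 12 months at zero correlation but read 14-18 months at correlation 0.6-0.8. That shows the direction of the Kaplan-Meier bias; the size does not carry over to three scan dates.

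**5. Crossover.** As a bounding case, controls take the experimental hazard after PSA progression (continuous detection, 24-month cap). Power is about 0.50-0.70 with full scanning and 0.52-0.71 with 50% loss.

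**6. Type I error.** With no effect on either endpoint, equal loss gives rejection of 0.09-0.12. At the scan dates, a postulated 25% control and 75% radium-223 loss gives 0.04-0.25 (HR 0.89-1.09), and the reverse gives 0.03-0.18 (HR 0.93-1.13).

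**The case against.** The strongest reply is that the plan already states the right rule. Section 12.6 runs assessments to radiographic progression or death, so radiographic is the natural reading of the exemption, and section 7 is silent on later scans without forbidding them. That stands as far as it goes: this is a gap between sections, and a reader who inferred that the plan chose to stop scanning, or that the scans will certainly be missed, would go beyond the text. But sites work from section 7 and the calendar, neither repeats the promise, and the exempting term is undefined.

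Second, the PSA stopping rule also requires castrate testosterone. After C8D1 that is scheduled only at C13D1, not at cycles 9-12 or 14-17. C8D1 and C13D1 are also the visits with both CT/MRI and bone scan. This narrows the window. It does not close it, since unscheduled tests or an earlier value could be used.

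Third, a reader might infer that continued scanning would restore the lost power. That depends on the effect persisting after PSA progression. Section 7.10 lets controls start radium-223 then, and under full crossover nothing is recovered. This objection stands.

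Fourth, a reader might infer that the test is anti-conservative or favors radium-223. The documents do not support that. Clear inflation needs loss that differs by arm, through the share not scanned or the timing of PSA progression, and nothing in the documents shows such a difference.

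**Conclusion.** The inconsistency is in the text and should be fixed. If sites follow section 7 in preference to the sentence in 12.6, censoring of the primary endpoint depends on worsening disease, with fewer radiographic events, rPFS curves that tend to read too high, and a hazard ratio biased in a direction that cannot be predicted.

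The size is not derivable from the documents. The 50% row above is an illustration that rests on equal loss in both arms, no crossover and the assumed link between PSA and radiographic progression. It also credits day 699 with detecting bone progression, although no bone scan is scheduled then, so it overstates both the baseline and what continued scanning would recover. Deaths still count as events, which limits the damage. The case for change is freedom from bias and consistency with the intention-to-treat principle. A claim of large power loss or of type I error above 0.10 would need data that the documents do not contain.

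**What to change.** 1. In 12.6 and the synopsis, replace *death or investigator assessed progression* with *death or radiographic progression*.
2. Reconcile 7.10 (including its paragraph on subjects who stop at their own request), footnote 14 and the calendar with 12.6. The C8D1, C13D1 and C17D28 imaging already scheduled, with bone scans at their own scheduled times, should continue for every consenting subject without radiographic progression, regardless of PSA progression or treatment discontinuation.
3. Report by arm the number censored after treatment stopped without later imaging. Add one rPFS sensitivity analysis that counts PSA-based discontinuation without later imaging as an event. Inverse-probability-of-censoring weighting is optional. Time to castration resistance does not serve this purpose: it is a different endpoint and its definition in 8.6 omits death.

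**Cost.** Protocol wording, one analysis and one count. No new imaging visit is needed, and day 699 falls within the existing two-year follow-up. The real burden is obtaining scans from subjects treated elsewhere. After C13D1 the change secures CT/MRI only. Scans not taken cannot be recovered at analysis, so the change is worth most when made early.

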### 12.7 Analysis of Secondary Objectives

Toxicity will be described within each arm by type, maximum grade and frequency among the safety population. The proportion of subjects in each arm with skeletal related events and secondary neoplasms will be reported individually and a mid p-value test will compare the proportions between arms.

Time to castration resistance (TTCR), PSA progression free survival (PCWG2 criteria), and Overall Survival (OS) will be reported by arm using Kaplan-Meier methods and tested using the log-rank test. The –time to castration resistance, the 2-year PSA PFS and OS proportions with 90% confidence intervals will be reported using Kaplan-Meier methods. Analyses will be completed on the ITT population.

Binomial proportions with 90% binomial confidence intervals of subjects who achieve PSA  $\leq$  0.2 ng/mL at 7 months after treatment initiation will be reported by arm. Similarly, the proportions and associated confidence intervals of subjects who achieve PSA  $\leq$  4 ng/mL at 7 months after treatment initiation will be described.

We will evaluate the distribution of pre-randomization marker levels (ALP and bone markers) among those who have and have not started ADT prior to randomization. If it appears that the prior initiation of ADT impacts the study entry bone marker levels to a fair extent, then all marker analyses will be conducted stratified by ADT initiation status. Descriptive statistics by arm will report the time to ALP progression among all subjects using Kaplan-Meier methods. ALP and serum bone markers will be reported by arm for each time-point using means or medians and corresponding measures of variability for all subjects with serum. Percentage change in ALP from baseline and changes from baseline in bone markers will be calculated for each later time point and tested between arms using a t-test or Wilcoxon rank test. If there is sufficient data, a mixed model will be used to model each endpoint over time to determine if the changes are different between treatment arms. Exploratory analysis will use separate Cox models with rPFS, PSA PFS, TTCR, and OS as the individual outcomes and treatment group, one marker, and the interaction between treatment and marker as independent covariates to find associations with outcomes. These models can be expanded to include other subject factors to determine if the marker contributes to outcome above subject factors that are known to be associated with the outcome. Similarly, logistic models can be used with 7-month PSA outcomes. The model analyses are considered exploratory for this trial. Thus, they are not powered and will not use multiple comparisons adjustments.

Worst pain will be reported from the BPI (SF) at each time point with a mean or median and the associated measure of variability and tested between arms with a t-test or Wilcoxon rank test. Comparisons at the times post-baseline will be compared between treatment arms using a paired test (t-test or Wilcoxon rank test.) WHO will be reported categorically by arm at each time point and tested between arms using the Mantel-Haenszel chi-square test. The change in WHO score from baseline will be calculated and be the outcome in a cumulative logistic model. Treatment arm will be included as an independent covariate to test if the change in pain is different between arms. Each post-baseline measure will be a separate model.

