### **2.2 Secondary Objectives**

2.2.1 Assess safety and toxicity including incidence of skeletal related events (SRE) and secondary neoplasms.

2.2.2 Estimate the proportion of subjects with  $PSA \leq 0.2$  ng/mL after 7 months of androgen deprivation therapy, the proportion of subjects with  $PSA \leq 4$  ng/mL after 7 months of androgen deprivation therapy, the median time to castration resistance, 2-year PSA progression free survival proportion (PCWG2 criteria) and 2-year overall survival proportion in both arms.

2.2.3 Determine the proportion of subjects with elevated serum total alkaline phosphatase (ALP) at baseline who normalize their alkaline phosphatase after 12 weeks of therapy, assess time to ALP progression ( $\geq 25\%$  increase in ALP from baseline/nadir (whichever is lower) and above ULN), association of ALP x in both arms.

2.2.4 Evaluate change in pain level and analgesic use using the Brief Pain Inventory (BPI short form) and WHO ladder scale, respectively, with therapy.

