### **8.10 Time to First SSRE**

From time of randomization to occurrence of first SSRE as defined in 10.10.

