## **11.2 Adverse Event (AE) Reporting**

### **11.2.1 Site Requirements for Recording Adverse Events**

Adverse events (AEs) will be recorded from the time of consent and for 30 days after the last dose of study drugs, regardless of whether or not the event(s) are considered related to the study drugs. The descriptions and grading scales found in the revised NCI Common Terminology Criteria for Adverse Events (CTCAE) v4 will be utilized for AE reporting. A copy of the CTCAE v4 can be downloaded from the CTEP website at <http://ctep.cancer.gov>.

All AEs considered related to study drug will be followed until resolution, return to baseline, or deemed clinically insignificant, even if this occurs post-trial.

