## **12. STATISTICAL CONSIDERATIONS**

### **12.1 Study Design**

Newly diagnosed metastatic prostate cancer subjects with  $\geq 2$  bone metastases will be accrued and randomized 1:2 to ADT without or with Radium-223 dichloride respectively. The primary aim of the study is to determine if the addition of Radium-223 dichloride to ADT will improve efficacy in this prostate cancer population. The primary efficacy endpoint is radiographic progression-free survival (rPFS). We expect the control arm with ADT alone to have a 12 month median rPFS. The addition of radium-223 to ADT will target an improvement of 7 months for a median rPFS of 19 months. A total of 140 events are required for at least 90% power to detect Hazard Ratio of 0.632 with a one-sided alpha of 0.1. The study powering is based on assumptions of 19 months median rPFS in the experimental arm and 12 months median rPFS in the control arm. Assuming exponential time to event data, a yearly dropout rate of 10% with

accrual in 24 months and study duration of 48 months, 204 subjects will provide 90% power with a 10% one-sided type I error. Hypothesis testing for the primary endpoint will be conducted at a one-sided 0.10 significance level using a stratified log-rank test. Randomization of 68 subjects to the ADT arm and 136 subjects to the ADT+R arm will be completed with stratification by extent of disease (<6 skeletal metastases without visceral disease versus  $\geq 6$  skeletal metastases or visceral disease) and baseline alkaline phosphatase (normal versus abnormal), abnormal alkaline phosphatase defined as  $> 130$  IU/L. If time anticipated for the number of events required for analysis significantly exceeds 48 months, the sponsor may enroll additional subjects to reach required number of events.

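### Skeletal events are compared as crude proportions with no time horizon, time to first SSRE is defined but never analysed, and SRE collection after treatment is not secured

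*Combined protocol and SAP*

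**What the plan says.** Section 2.2.1 sets the objective: "Assess safety and toxicity including incidence of skeletal related events (SRE) and secondary neoplasms". Section 12.7 reports the proportion of subjects with each event by arm, and "a mid p-value test will compare the proportions between arms"; the synopsis repeats this. No horizon, exposure adjustment, censoring rule, treatment of death or significance level is given for that test. The same section uses Kaplan-Meier and log-rank methods for castration resistance, PSA progression-free survival and overall survival.

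Section 8.9 defines the SSRE, and section 8.10 defines time to first SSRE: "From time of randomization to occurrence of first SSRE as defined in 10.10". The protocol has no section 10.10; the definition is in 8.9. Time to first SSRE appears in no objective, outcome measure or analysis.

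On data collection:
- Section 7.10 ends protocol therapy at radiologic progression, symptomatic deterioration or PSA-defined castration resistance. It then follows subjects in both arms every 3 months to 2 years from randomization.
- Section 11.2.1 says "Adverse events (AEs) will be recorded from the time of consent and for 30 days after the last dose of study drugs".
- Section 7.10 and calendar footnote 14 ask for later adverse event data only where medical record review makes them available. The calendar does tick the adverse event row in the follow-up column.
- The calendar's follow-up block lists survival and secondary malignancies. The section 7.10 paragraph on subjects who ask to stop therapy likewise says "subjects will continue to be followed for survival status and for secondary malignancies". Neither names SREs.

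**The concern.** A crude proportion depends on how long each subject was watched. SRE recording is mandatory only around treatment, and treatment stops at progression, which is the event radium is meant to delay. If later SREs are caught haphazardly, the arm with longer radiographic progression-free survival (rPFS) has more time in which an SRE can be counted. The comparison then leans against that arm and can hide part of a true SRE benefit. The protocol already defines an endpoint that deals with time and then leaves it unused. SRE incidence belongs to the first secondary objective and gets a formal between-arm test, so it will be read as a result.

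**Working it through.** **1. The plan's own figure.** There is no power or sample size for SREs. The primary calculation can be checked: "A total of 140 events are required for at least 90% power to detect Hazard Ratio of 0.632 with a one-sided alpha of 0.1". By Schoenfeld with 1:2 allocation, events = (1.2816 + 1.2816)² / [(1/3)(2/3)(ln 0.632)²] = 6.570 / (0.2222 × 0.2106) = 140.4. This agrees, so the planning medians of 12 and 19 months are a sound base.

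**2. Inputs.** Progression hazards are ln2/12 = 0.0578 per month (control) and ln2/19 = 0.0365 (radium). The cap is 24 months of follow-up. The documents give no SRE rate in this population, so the SRE hazard is an assumption: 0.01, 0.02 or 0.03 per month (a 24-month risk of 21%, 38% or 51% with complete capture). Times are taken as exponential and independent, and SRE capture as ending at progression or 24 months.

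**3. Observation time.** (1 − exp(−24 × λp))/λp = 13.0 months (control) v 16.0 months (radium).

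**4. Crude proportion with an SRE.** P = λs/(λs + λp) × [1 − exp(−24(λs + λp))]. Worked case with λs = 0.02:
- Control: 0.02/0.0778 × (1 − 0.155) = 21.7%.
- Radium, equal hazard: 0.02/0.0565 × (1 − 0.258) = 26.3%.
- Radium at hazard ratio (HR) 0.61: 0.0122/0.0487 × (1 − 0.311) = 17.3%.

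The 0.61 is the SRE hazard ratio that section 1.3 quotes from the phase 3 trial in castration-resistant disease. It is a scenario only.

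| Control SRE hazard per month | Control | Radium, HR 1.00 | Radium, HR 0.61 | Crude ratio at HR 0.61 | HR at which the arms look equal |
|---|---|---|---|---|---|
| 0.01 | 11.9% | 14.5% | 9.2% | 0.77 | 0.80 |
| 0.02 | 21.7% | 26.3% | 17.3% | 0.79 | 0.80 |
| 0.03 | 30.0% | 36.0% | 24.4% | 0.81 | 0.79 |

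Part of the move from 0.61 to 0.77–0.81 comes only from comparing risks instead of hazards. With complete 24-month capture the risk ratio, (1 − exp(−24 × 0.61λs))/(1 − exp(−24λs)), is 0.64 to 0.69. The rest is unequal observation.

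**5. Adding the planned 10% yearly dropout.** Observation becomes 12.0 v 14.6 months. Over control 24-month risks of 10% to 50%, the crude ratio is 1.19 to 1.22 at HR 1.00 and 0.75 to 0.80 at HR 0.61. The arms look equal at HR 0.80 to 0.82. With 68 and 136 subjects and an assumed two-sided 0.05 mid-p test, radium is called worse in 3.6% to 10.9% of trials at HR 1.00 (nominal 2.5% per tail), and in at most 0.6% at HR 0.61. Adding the 30-day tail at 20% and 40% risk leaves the pattern unchanged.

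**6. If every SRE to 24 months were captured.** With equal survival, the arms are observed equally. With a death HR of 0.695 (same phase 3 trial) and control median survival of 32.2 to 44 months (section 1.5), crude SRE proportions at equal hazard differ by 0.8 to 1.9 points at 20% to 40% risk.

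**7. Power at HR 0.61, two-sided 0.05.** With capture ending at progression, there are about 9 to 48 SREs: 10% to 37% by log-rank against 7% to 13% by mid-p. With full 24-month capture and no dropout or death (an upper bound), events are 68 × 0.213 + 136 × 0.136 = 33 up to 68 × 0.513 + 136 × 0.355 = 83. Power is Φ(√(events × 2/9) × 0.494 − 1.96), or 27% to 57%.

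**The case against.** The strongest reply is that unequal observation is not the written rule. Both arms are followed every 3 months to 2 years from randomization, including after progression, and the calendar ticks the adverse event row in that period. This stands: capture ending at progression is an inference from the 30-day window and from the optional wording on later data. Sites that retrieved every SRE to 24 months would leave only the small differences in step 6. The protocol does not require them to do so.

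Second, rPFS medians are only a proxy for time on therapy. PSA-defined castration resistance also ends it, and section 5.5.3 leaves ADT after seven cycles to the treating physician. This also stands, so the figures are indicative.

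Third, the objective is incidence under safety, which a proportion answers, and time to first SSRE was never promised as an objective. That is fair, but an incidence proportion still needs a horizon and a collection window, and 8.10 should be used or removed.

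Fourth, a time-to-event analysis alone would not cure the problem. If SREs cluster around progression and capture stops there, the censoring is informative. This is right, and it is why data collection comes first in the fix.

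A reader might also infer that an effective radium arm must look worse on SREs by construction. The figures do not support that: it requires longer rPFS together with an SRE hazard ratio above about 0.8. Nor does the bias carry over to secondary neoplasms, which are already collected to 2 years in both arms. Only differential death or dropout matters there, about 0.1 to 0.3 points at 2% to 5% risk under the survival scenarios of step 6.

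**Conclusion.** The point holds for SREs, as a gap in analysis and data collection that should be closed. Section 12.7 makes a formal comparison without a time horizon, censoring rule or handling of death. Section 8.10 is unused, and SRE ascertainment after treatment is left to chance. If capture follows time to progression, the crude comparison is biased against the arm with longer rPFS: a ratio of about 1.2 where the hazards are equal, and about 0.77 to 0.81 where the true hazard ratio is 0.61. That is a dilution, not a reversal. The size rests on assumed SRE hazards, exponential and independent times, the planning medians as a proxy for time under observation, and capture that stops at progression. The documents permit that last condition but do not state it. No bias claim is made for secondary neoplasms.

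**What to change.** 1. Data first. In section 7.10 and the calendar, name SSREs among the items asked at the existing 3-monthly contact, to 24 months from randomization in both arms and regardless of progression.
2. In section 12.7, analyse time to first SSRE from randomization in the ITT population. Report cumulative incidence with death as a competing event (for example at 24 months). Compare the cause-specific hazards with the stratified log-rank test, censoring at the last SSRE assessment. State the level and sidedness of the test. The log-rank test addresses the cause-specific hazard, not the cumulative incidence, and the text should say so.
3. Keep the crude SRE proportions as description.
4. In section 8.10, correct the reference from 10.10 to 8.9 and add the censoring rule.

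Cost: one more question per contact and a little more analysis. Power for SREs stays low either way, so the gain is an interpretable estimate more than a decisive test. Section 7.10 allows control subjects to start radium-223 after leaving protocol therapy, so an analysis that counts later events compares treatment policies and should be described that way.
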